12 AUDITING AND MONITORING

Sponsor-assigned monitors will conduct regular site visits to the investigational facilities for the purpose of monitoring various aspects of the study, such as assessing patient enrollment, compliance with protocol procedures, completeness and accuracy of data entered into the eCRFs, verification of eCRF data against original source documents, and occurrence of AEs. The investigator must agree to sponsor-authorized personnel having direct access to the clinical (or associated) files and clinical study supplies (dispensing and storage areas) to ensure compliance with applicable regulations, and the investigator will assist with the sponsor's monitoring activities.

Quality control will occur at each stage of data handling to ensure that all data are reliable and have been processed correctly. The sponsor should ensure oversight of any study-related duties and functions carried out on its behalf, including study-related duties and functions that are subcontracted to another party by the sponsor's contracted CRO(s).

The eCRFs should be completed in a timely manner and on an ongoing basis to allow regular review by the study monitor.

Details describing the strategy, responsibilities, and requirements of the study monitoring are provided in the Study Monitoring Plan.

The purpose of an audit is to assess whether ethics, regulatory, and quality requirements are being fulfilled. The sponsor or its representative may conduct audits at the investigative sites including, but not limited to, drug supply, presence of required documents, the informed consent process, and comparison of eCRFs with source documents. Government regulatory authorities may also inspect the investigator during or after the study. The investigator (or designee) should contact the sponsor/CRO immediately if this occurs. All medical records (progress notes) must be available for audit. The investigator must agree to participate with audits conducted at a convenient time in a reasonable manner.

12.1 Risk and Quality Tolerance Limits

The sponsor will review risk control measures outlined in the study-specific monitoring plan periodically to ascertain whether the implemented clinical quality management activities remain effective and relevant. The clinical quality management approach and any important deviations from the predefined quality tolerance limits and remedial actions adopted will be described in the clinical study report (CSR).

12.2 Protocol Adherence and Deviations

The investigator and site personnel should conduct the study in compliance with the protocol and should use continuous vigilance to identify and report protocol deviations.

A protocol deviation is any change, divergence, or departure from the study design or procedures defined in the protocol that may be on the part of the investigator, site personnel, or the patient.

Important protocol deviations are a subset of protocol deviations that may significantly impact the completeness, accuracy, and/or reliability of the study data or that may significantly affect a patient's rights, safety, or well-being. For example, important protocol deviations may include enrolling patients in violation of key eligibility criteria designed to ensure a specific patient population or failing to collect data necessary to interpret primary endpoints, as this may compromise the scientific value of the study.

The investigator should not implement any deviation from the protocol without agreement from the sponsor and prior review and approval from the IRB of an amendment, except where necessary to eliminate an immediate hazard to a study patient, or when the change involves only logistical or administrative aspects of the study, such as a change in a monitor or telephone number.

In the event of an important protocol deviation, the investigator will discuss the deviation with the sponsor's medical monitor and will come to an agreement as to whether the patient should be withdrawn from the study due to the important protocol deviation.

13 AMENDMENTS

Protocol modifications, except those intended to reduce immediate risk to study patients, may be made only by the sponsor. A protocol change intended to eliminate an apparent immediate hazard to patients should be implemented immediately.

Any permanent change to the protocol must be handled as a protocol amendment. The written amendment must be submitted to the IRB, and the investigator must await approval before implementing the changes. The sponsor will submit protocol amendments to the appropriate regulatory authorities for approval.

The current version of the ICF will require similar modification if the IRB, investigator, and/or sponsor, judge the amendment to the protocol to substantially change the study design and/or increase the potential risk to the patient and/or impact the patient's involvement as a study patient. In such cases, the ICF will be renewed for enrolled patients before their continued participation in the study.

14 STUDY REPORT AND PUBLICATIONS

This study will be registered on ClinicalTrials.gov in accordance with applicable laws or publication policy and may also be registered on other publicly accessible websites, as necessary.

The sponsor is responsible for preparing and providing the appropriate regulatory authorities with the CSR according to the applicable regulatory requirements. The sponsor should ensure that the CSR meets the standards of the ICH Guideline for Structure and Content of CSR (ICH E3).

The publication policy of the sponsor is discussed in the investigator's clinical research agreement.

The results of this study may be published or presented at scientific meetings. If this is foreseen, the investigator agrees to submit all manuscripts or abstracts to the sponsor before submission. This allows the sponsor to protect proprietary information and to provide comments.

The sponsor will comply with the requirements for publication of study results. In accordance with standard editorial and ethical practice, the sponsor will generally support publication of multicenter studies only in their entirety and not as individual site data. In this case, a coordinating investigator will be designated by mutual agreement.

Authorship will be determined by mutual agreement and in line with International Committee of Medical Journal Editors authorship requirements.

15 STUDY START AND TERMINATION

The study start date is the date on which the first patient provides informed consent.

The end of the study is defined as the last patient's last assessment.

This study may be terminated prematurely in whole or in part due to a change in the benefit/risk profile for ATI-1777 such that continuation of the study would not be justified on medical or ethical grounds. This determination may be made by the study investigators in conjunction with the sponsor, or by the IRB or the US FDA. The sponsor may also elect to terminate the study if enrollment is sufficiently slow to prevent the completion of the study in an acceptable timeframe, or if ATI-1777 development is discontinued. Both the sponsor and the investigator reserve the right to terminate the study or the participation in the study at an investigator's site at any time. In terminating the study, the sponsor and the investigator will assure that adequate consideration is given to the protection of the patients' interests.

If the study is prematurely terminated or suspended for any reason, the sponsor/investigator/site personnel should promptly inform the study patients and should assure appropriate therapy and follow-up for the patients. Where required by the applicable regulatory requirements, the IRB should be informed promptly and be provided with a detailed written explanation of the termination or suspension.

If the investigator terminates or suspends a study without prior agreement of the sponsor, the investigator should inform the site personnel. The investigator/site personnel should promptly inform the sponsor and the IRB. The investigator/site personnel should also provide the sponsor and the IRB a detailed written explanation of the termination or suspension.

16 CONFIDENTIALITY

All information generated in this study is considered highly confidential and must not be disclosed to any person or entity not directly involved with the study unless prior written consent is gained from the sponsor. However, authorized regulatory officials, IRB personnel, and the sponsor and its authorized representatives are allowed full access to the records.

All study patients must be informed that their personal study-related data will be used by the sponsor in accordance with local data protection law. The patients must be informed that their medical records may be examined by auditors or other authorized personnel appointed by the sponsor, by appropriate IRB members, and by inspectors from regulatory authorities.

Identification of patients and eCRFs shall be by unique patient identification numbers (such as randomization number) only. All personal identifiers according to applicable regulations (e.g., name, telephone number) must be redacted permanently by the site personnel and replaced with the patient's unique identification number in all records and data before transfer to the sponsor (or designee).

All personal details will be treated as confidential by the investigator and staff at PRA.

APPENDIX 2 - PATIENT INSTRUCTIONS

Preparation and General Instructions:

1. Reminder to:
 - a) Refrain from bathing, swimming and/or participating in strenuous exercise that would cause profuse sweating for 6 hours after application of study medication.
 - b) Refrain from applying moisturizers, emollients, and sunscreen to AD treatment areas for the duration of protocol therapy. Moisturizers, emollients, and sunscreens may be applied to non-AD treatment areas.
 - c) Refrain from excessive sun exposure (e.g., sunbathing and/or tanning salon visits) and minimize sun exposure (e.g., wear sun protective clothing, hat) as much as possible.
2. Gather a clean washcloth and towel, the study medication bottle, and dropper.
3. Skin should be clean and dry before applying study medication.
4. Wash your hands with soap and water before and after using this study medication.
5. Record your 'worst' itch over the previous 24 hours on your diary in the morning before applying study medication.
6. Apply a thin layer of study medication to the identified AD target skin area as instructed by the study doctor or the study staff. Keep applying study medication to the area throughout the study, even if the skin begins to clear. If new areas of AD appear, study medication may be applied to these areas.
7. Avoid study medication contact with the eye.
8. You will apply study medication twice a day, approximately 8 to 12 hours apart.
9. Document on your diary whether you completed the morning and/or evening dose and total amount of drug (mL) applied at each application timepoint.
10. Remember to bring your study medication bottles both used and unused to each study visit along with your diary.

Study Medication Application:

1. Draw up exactly 1 mL of study medication into the dropper. The medication level should be at the 1-mL line.
2. During study medication application, avoid any study medication running into your eyes.
3. Squeeze a few drops of study medication onto the center of the identified target AD area and gently rub the study medication into your skin. Keep applying a few drops and rubbing into your skin until **the entire area** is covered with a thin film of study medication.
4. Draw up additional medication 1 mL at a time to cover the entire AD area. No more than a total of 8 mL should be used to treat all affected areas. Less than 8 mL may be used if a lower amount is sufficient to cover all affected skin areas.
5. Place the dropper back on the bottle and make sure it is closed tightly.
6. Document the total amount of mL used at each application timepoint on your diary.
7. It is important to continue to apply study medication to the target AD areas throughout the study, even if the skin begins to clear.

8. Wash your hands after using this product to prevent any residue being left on your hands.
9. If you missed a dose or doses, record the missed dose or doses in your diary and tell the study staff at your next visit.

Missed Doses: If you miss a dose of this study medicine, apply it as soon as possible. However, if it is almost time for your next dose, skip the missed dose, and go back to your regular dosing schedule.

Storage: Store the medicine in the original glass bottle in the carton provided at room temperature, away from heat, moisture, and direct light. Keep from freezing. Keep out of the reach of children.

APPENDIX 3 - HANIFIN AND RAJKA DIAGNOSTIC CRITERIA FOR ATOPIC DERMATITIS ([HANIFIN AND RAJKA 1980](#))

Major criteria: Must have 3 or more of the following:

1. Pruritus
2. Typical morphology and distribution
 - Flexural lichenification or linearity in adults
 - Facial and extensor involvement in infants and children
3. Chronic or chronically relapsing dermatitis
4. Personal or family history of atopy (asthma, allergic rhinitis, AD)

Minor criteria: Should have 3 or more of:

1. Xerosis
2. Ichthyosis, palmar hyperlinearity, or keratosis pilaris
3. Immediate (Type 1) skin-test reactivity
4. Raised serum IgE
5. Early age of onset
6. Tendency toward cutaneous infections (especially *S aureus* and herpes simplex) or impaired cell-mediated immunity
7. Tendency toward non-specific hand or foot dermatitis
8. Nipple eczema
9. Cheilitis
10. Recurrent conjunctivitis
11. Dennie-Morgan infraorbital fold
12. Keratoconus
13. Anterior subcapsular cataracts
14. Orbital darkening
15. Facial pallor or facial erythema
16. Pityriasis alba
17. Anterior neck folds
18. Itch when sweating
19. Intolerance to wool and lipid solvents
20. Perifollicular accentuation
21. Food intolerance
22. Course influenced by environmental or emotional factors
23. White dermographism or delayed blanch

APPENDIX 4 - POSSIBLE HY'S LAW LIVER CHEMISTRY ACTION AND FOLLOW-UP ASSESSMENTS

Suggested Actions and Follow-up Assessments ¹	
Actions	Follow-up Assessments

• Immediately discontinue study medication.• Report the event to the sponsor or designee within 24 hours.• Complete an SAE data collection tool if the event also met the criteria for an SAE.²• Perform liver chemistry follow-up assessments.• Monitor the participant until liver chemistry test abnormalities resolve, stabilize, or return to baseline (see MONITORING below).• Do not restart/rechallenge participant with study treatment unless allowed per the protocol and sponsor approval is granted.• If restart/rechallenge is either not allowed per the protocol or not granted, permanently discontinue study treatment. The participant may continue in the study for any protocol-specified follow-up assessments. 
MONITORING: If ALT $\geq 3 \times \text{ULN}$ AND bilirubin $\geq 2 \times \text{ULN}$ or INR > 1.5:
 
• Repeat liver chemistry tests (ALT, AST, alkaline phosphatase, bilirubin) and perform liver event follow-up assessments within 24 hours.• Monitor participant twice weekly until liver chemistry test abnormalities resolve, stabilize, or return to baseline.• A specialist or hepatology consultation is recommended. 
If ALT $\geq 3 \times \text{ULN}$ AND bilirubin $< 2 \times \text{ULN}$ and INR ≤ 1.5:
 
• Repeat liver chemistry tests (include ALT, AST, alkaline phosphatase, bilirubin) and perform liver chemistry follow-up assessments within 24 to 72 hours.• Monitor participants weekly until liver chemistry abnormalities resolve, stabilize, or return to baseline.	
• Viral hepatitis serology³• Obtain INR and recheck with each liver chemistry assessment until the transaminases values show downward trend• Obtain blood sample for ATI-1777 drug concentration⁴• Serum CPK and lactate dehydrogenase• Fractionate bilirubin, if total bilirubin $\geq 2 \times \text{ULN}$• Obtain complete blood count with differential to assess eosinophilia• Record the appearance or worsening of clinical symptoms of liver injury, or hypersensitivity, on the AE eCRF• Record use of concomitant medications (including acetaminophen, herbal remedies, and other over-the-counter medications) on the concomitant medications eCRF 
If ALT $\geq 3 \times \text{ULN}$ AND bilirubin $\geq 2 \times \text{ULN}$ or INR > 1.5:
 
• Anti-nuclear antibody, anti-smooth muscle antibody, Type 1 anti-liver kidney microsomal antibodies, and quantitative total immunoglobulin G or gamma globulins.• Serum acetaminophen adduct high performance liquid chromatography assay (quantifies potential acetaminophen contribution to liver injury in participants with definite or likely acetaminophen use in the preceding week [James et al 2019]).

AE = adverse event; ALT = alanine aminotransferase; AST = aspartate aminotransferase; CPK = creatine phosphokinase; eCRF = electronic case report form; INR = international normalized ratio; SAE = serious adverse event; ULN = upper limit of normal

1. Serum bilirubin fractionation should be performed if testing is available. If serum bilirubin fractionation is not immediately available, discontinue study treatment if $ALT \geq 3 \times ULN$ **and** bilirubin $\geq 2 \times ULN$. Additionally, if serum bilirubin fractionation testing is unavailable, **record the absence/presence of detectable urinary bilirubin on dipstick** which is indicative of direct bilirubin elevations suggesting liver injury.
2. All events of $ALT \geq 3 \times ULN$ **and** bilirubin $\geq 2 \times ULN$ ($>35\%$ direct bilirubin) or $ALT \geq 3 \times ULN$ **and** INR >1.5 may indicate severe liver injury (**possible 'Hy's Law'**) **and must be reported as an SAE (excluding studies of hepatic impairment or cirrhosis)**. The INR measurement is not required and the stated threshold value will not apply to participants receiving anticoagulants.
3. Hepatitis A immunoglobulin M antibody; hepatitis B surface antigen and hepatitis B core antibody; hepatitis C ribonucleic acid; cytomegalovirus immunoglobulin M antibody; Epstein-Barr viral capsid antigen immunoglobulin M antibody (or, if unavailable, heterophile antibody or monospot testing); and hepatitis E immunoglobulin M antibody.
4. Drug concentration sample may not be required for participants known to be receiving placebo or non-comparator treatments. Record the date/time of the blood sample draw and the date/time of the last dose of study treatment prior to the blood sample draw in the eCRF. If the date or time of the last dose is unclear, provide the participant's best approximation. If the date/time of the last dose cannot be approximated, do not obtain a blood sample. Instructions for sample handling and shipping are in the reference manual.

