5.4 Premature Discontinuation

5.4.1 *Premature Discontinuation of Study Medication*

Patients should be permanently discontinued from study medication in the event of any of the following:

- The patient experiences significant worsening of AD such that additional therapy for the treatment of AD is required
- Confirmed, active infection with the SARS-CoV-2 virus
- Infection requiring parenteral antimicrobial therapy or hospitalization
- Symptomatic herpes zoster
- Malignancy – except for nonmelanoma skin cancer not in or near the treatment area
- Anaphylactic or severe allergic reaction
- WBC count: $<1 \times 10^9/L$ or second occurrence of $<2 \times 10^9/L$ – in each case, value should be confirmed by retesting before treatment discontinuation

- ANC: $<0.5 \times 10^9/L$ or second occurrence of $<1 \times 10^9/L$ – in each case, value should be confirmed by retesting before treatment discontinuation
- Lymphocyte count: $<0.3 \times 10^9/L$ or second occurrence of $<0.5 \times 10^9/L$ – in each case, value should be confirmed by retesting before treatment discontinuation
- Platelet count: $<50 \times 10^9/L$ or second occurrence of $<75 \times 10^9/L$ – in each case, value should be confirmed by retesting before treatment discontinuation
- Hemoglobin: $<6.5 \text{ g/dL}$ or second occurrence of $<8 \text{ g/dL}$ – in each case, value should be confirmed by retesting before treatment discontinuation
- AST or ALT:
 - $5 \times \text{ULN}$ persisting for 2 weeks of study medication interruption or second event of $>5 \times \text{ULN}$
 - $>3 \times \text{ULN}$ and (total bilirubin $>2 \times \text{ULN}$ or international normalized ratio [INR] of >1.5)
 - $3 \times \text{ULN}$ with total bilirubin $>2 \times \text{ULN}$ or symptoms of hepatocellular injury [fatigue, nausea, vomiting, right upper quadrant pain or tenderness, fever, rash and/or eosinophilia ($>5\%$)].
- Any patient who develops any of the following ECG findings during the active treatment phase will be instructed to stop study medication and will be withdrawn from the study:
 - Clinically significant rhythm disturbance other than sinus rhythm or ectopic supraventricular rhythm (ectopic atrial rhythm).
 - Clinically significant conduction disturbance including PR $>240 \text{ msec}$, pre-excitation (delta wave and PR $<120 \text{ msec}$), second degree or higher atrioventricular block.

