6.3.2.1 Potential Drug-induced Liver Injury

Hy's Law cases have the following 3 components:

1. The drug causes hepatocellular injury, generally shown by a higher incidence of ≥ 3 -fold elevations above the ULN of ALT or AST than the placebo
2. Among study patients showing such aminotransferase elevations, often with aminotransferases much greater than $3 \times \text{ULN}$, one or more also shows elevation of serum total bilirubin to $> 2 \times \text{ULN}$ or INR > 1.5 , without initial findings of cholestasis (elevated ALP)
3. No other reason can be found to explain the combination of increased aminotransferase and total bilirubin, such as viral hepatitis A, B, or C; evidence for biliary obstruction; acute alcoholic hepatitis (recent drinking and AST $> 2 \times \text{ALT}$ are supportive); recent history of severe hypotension or congestive heart failure; other underlying viral disease; pre-existing or acute liver disease; or another drug (including non-prescription products such as herbal supplements) capable of causing the observed injury

During the study, the investigator will remain vigilant for increases in liver biochemistry. The investigator is responsible for determining whether a patient meets potential drug-induced liver injury criteria at any point during the study.

In the event that a patient shows laboratory results of:

- AST or ALT: $> 5 \times \text{ULN}$ persisting for 2 weeks after study medication interruption or second occurrence of $> 5 \times \text{ULN}$
- $\geq 3 \times \text{ULN}$ and (total bilirubin $\geq 2 \times \text{ULN}$ or INR > 1.5)
- $\geq 3 \times \text{ULN}$ with appearance of fatigue, nausea, vomiting, right upper quadrant pain or tenderness, fever, rash and/or eosinophilia ($> 5\%$)

Please refer to [Appendix 4](#) for further information.

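### The only automatic SAE rule for possible Hy's Law names ALT alone, although the protocol's liver triggers cover ALT or AST

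*Protocol*

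**What the plan says.** Protocol 5.4.1 (Premature Discontinuation of Study Medication) has one list item for AST or ALT. Under it sits a trigger of more than 3 × ULN together with total bilirubin above 2 × ULN "or international normalized ratio [INR] of >1.5".

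Protocol 6.3.2.1 describes Hy's Law in three components. The first concerns a higher incidence of 3-fold or greater "elevations above the ULN of ALT or AST than the placebo". The section then lists laboratory triggers, the first of which names AST or ALT, and ends "Please refer to [Appendix 4](#) for further information".

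Protocol Appendix 4 is a table headed "Suggested Actions and Follow-up Assessments" with footnotes. Its first monitoring row asks for repeat tests within 24 hours and then "Monitor participant twice weekly until liver chemistry test abnormalities resolve, stabilize, or return to baseline". An extra work-up begins with "Anti-nuclear antibody, anti-smooth muscle antibody, Type 1 anti-liver kidney microsomal antibodies". Footnote 2 is the only part in mandatory terms about SAE status. Its bilirubin limb opens "All events of $ALT \geq 3 \times ULN$ and bilirubin $\geq 2 \times ULN" and its INR limb reads "ALT \geq 3 \times ULN$ and INR >1.5 may indicate severe liver injury". SAP Appendix 1 reproduces the table and footnotes. SAP 8.2 points the Hy's law stopping rule to that appendix, whereas Protocol 4.4.1 points it to 6.3.2.1.

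**The concern.** Elsewhere the protocol treats the two aminotransferases alike: in exclusion criterion 11, in the risk section (1.3.2.6), in 5.4.1, in Table 5 and in 6.3.2.1. Appendix 4 drops AST without giving a reason. Two patients can meet the same discontinuation trigger and yet differ in automatic SAE status only because of which enzyme rose.

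This matters because footnote 2 is the only provision that makes a possible Hy's Law case an SAE without further judgment; the seriousness criteria in 8.1.2 contain no such rule. SAE status starts the 24-hour safety report in 8.4 and enters the SAE rows of the adverse event summary (SAP 12.6.1). This is a first-in-human study of a class for which the protocol itself lists liver enzyme elevation as a risk.

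**Working it through.** There is no plan figure to reproduce. The check is a count of the text, followed by two test patients.

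**Count of enzyme thresholds in Protocol Appendix 4 (the same in SAP Appendix 1)**

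| Place | Condition | Enzyme named |
|---|---|---|
| Monitoring row 1 | ≥3 × ULN, bilirubin ≥2 × ULN or INR >1.5 | ALT |
| Monitoring row 2 | ≥3 × ULN, bilirubin <2 × ULN and INR ≤1.5 | ALT |
| Extra work-up | as row 1 | ALT |
| Footnote 1 | ≥3 × ULN and bilirubin ≥2 × ULN | ALT |
| Footnote 2, bilirubin limb | ≥3 × ULN and bilirubin ≥2 × ULN (>35% direct) | ALT |
| Footnote 2, INR limb | ≥3 × ULN and INR >1.5 | ALT |

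That is six statements in five places, and none names AST. Across both appendices it is 2 × 6 = 12 statements. AST appears in the appendix only as a test to repeat and in the abbreviation list.

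**Two AST-only patients** (values are hypothetical; enzymes and bilirubin in multiples of ULN)

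- Patient A: ALT 2.5, AST 4, bilirubin 2.5 (taken as over 35% direct), INR 1.1.
- Patient B: ALT 2.5, AST 4, bilirubin 1, INR 1.7.

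| Rule | Patient A | Patient B |
|---|---|---|
| 5.4.1 trigger, AST or ALT | met (4 > 3, 2.5 > 2) | met (4 > 3, 1.7 > 1.5) |
| Footnote 2, mandatory SAE | not met (ALT 2.5 < 3) | not met (ALT 2.5 < 3) |
| Row 1 read as ALT AND (bilirubin or INR) | not met | not met |
| Row 1 read as (ALT AND bilirubin) or INR | not met | met |
| Footnote 2 with ALT or AST | met | met |
| Row 1 with ALT or AST, bracketed | met | met |

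Row 2 fits neither patient: A has raised bilirubin, B has raised INR, and in both ALT is below 3 × ULN. The extra work-up follows row 1.

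The gap in the SAE rule is therefore certain on both limbs. The gap in the suggested schedule and work-up is certain only for raised bilirubin with INR at or below 1.5.

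**Difference in retesting for patient A.** Under 7.4.2 and Table 5, AST above 3 × ULN means the drug is held and the test repeated as soon as possible. If the result is confirmed, testing is weekly or sooner. Over 14 days the stated minimum is 14 / 7 = 2 weekly tests, against 2 × 14 / 7 = 4 under row 1.

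**Which limb scheduled tests can detect.** AST and total and direct bilirubin are in the panel listed in 6.3.2. INR is not; Appendix 4 asks for it as follow-up. Scheduled testing can thus find patient A but would not by itself find patient B.

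**The case against.** The strongest reply is that little is lost, and most of that reply stands. An AST-only patient is still covered by several provisions:

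- Study drug is stopped under 5.4.1, and the Hy's law stopping rule in 4.4.1 points to 6.3.2.1, not to the appendix.
- The general Appendix 4 actions carry no ALT condition, including the report to the sponsor within 24 hours. What is lost is the 24-hour repeat test, not that report.
- Section 8.1.4 requires a laboratory abnormality that leads to discontinuation to be recorded as an AE or SAE.
- Section 7.4.2 gives a prompt repeat and then at least weekly tests, 8.1.5 makes liver enzyme AEs events of special interest, and 8.1.2 allows SAE status by medical judgment.
- Footnote 1 loses nothing in practice, because its consequence (stopping drug) already follows from 5.4.1.

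Two limits on the argument also stand. Component 1 of 6.3.2.1 is a study-level statement about incidence against placebo, so it cannot serve as a threshold for one patient. The 6.3.2.1 bullet for 3 × ULN with bilirubin or INR names no enzyme. The patient-level basis is therefore 5.4.1. In addition, footnote 2 does not mirror the trigger list even for ALT: it adds the direct-bilirubin condition and omits the symptom and 5 × ULN triggers. Adding AST aligns the enzyme and nothing else.

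One could also say that ALT is the more liver-specific enzyme. The protocol does not give that reason. An isolated AST rise would still not become an automatic SAE after the change, since raised bilirubin or INR remains required. CPK, already in the follow-up list, helps identify a muscle source.

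A reader might infer that an AST-only case would stay on drug, go unreported or always miss the schedule. The provisions above rule out the first two. The third fails because row 1 has no brackets and, read literally, admits any patient with INR above 1.5.

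**Conclusion.** The point holds and is minor. The certain defect is that the one automatic SAE rule for possible Hy's Law omits AST on both limbs. In addition, the suggested 24-hour repeat, twice-weekly tests and extra work-up omit an AST-only patient with raised bilirubin and INR at or below 1.5. With INR above 1.5 the schedule and work-up are ambiguous.

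The practical size is one automatic SAE label and, for the bilirubin case, 4 rather than at least 2 tests in 14 days, plus the extra work-up. The documents give no rate for such events. That they will be very rare is a judgment from about 50 patients, half on vehicle, treated for 4 weeks.

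No efficacy analysis is affected. Because SAP 8.2 refers the stopping rule to the ALT-only copy, a reader might infer that the SAP narrows the rule. But 5.4.1 governs discontinuation and names both enzymes, so the mismatch should be tidied and does not show that patients would be handled differently.

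**What to change.** In Protocol Appendix 4, and then in SAP Appendix 1, replace ALT ≥3 × ULN with ALT or AST ≥3 × ULN in both monitoring rows, the extra work-up, footnote 1 and both limbs of footnote 2. Bracket the condition in row 1 and the extra work-up as (ALT or AST ≥3 × ULN) AND (bilirubin ≥2 × ULN or INR >1.5). Leave the rest of footnote 2 as it is, including the direct-bilirubin condition and the anticoagulant exception.

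The cost is a wording change at five places in each of two appendices. AST and total and direct bilirubin are already measured, so no new scheduled data are needed. The downside is at most an occasional extra SAE report or repeat test.
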